6.2. BASELINE

Unless otherwise specified, baseline of DB period is defined as the last non-missing measurement taken prior to reference start date (including unscheduled assessments). Unless otherwise specified, baseline of OL period is defined as the measurement at Visit 7.

Whenever available, the time information should be accounted for in the derivation of baseline values. In the case where time isn't available and the date of last non-missing measurement and the reference start date coincide, that measurement will be considered baseline.

Adverse Events (AEs) and medications commencing on the reference start date will be considered post-baseline.

6.3. DERIVED TIME POINTS

For subjects with missing SAPS-PD total score at Week 6 (Visit 7), a last observation carried forward (LOCF) endpoint for SAPS-PD total score will be derived (for use in sensitivity analysis), using the last post-baseline value up to the Week 6 visit date. Similarly, missing CGI-S score, missing NPI score, missing NPI (H+D) score and missing MMSE score are also imputed using the same LOCF method.

Both scheduled and unscheduled assessments that are collected post baseline will contribute to the derivation of LOCF endpoint.

LOCF imputation will be performed on data with the early termination data already mapped (see Section 6.4).

6.4. RETESTS, UNSCHEDULED VISITS AND EARLY TERMINATION DATA

In general, for by-visit summaries, data recorded at the scheduled visits will be presented.

Unscheduled measurements will not be included in by-visit summaries. Unscheduled measurements collected prior to the first dose of study medication will contribute to the derivation of the baseline value. Unscheduled measurements collected post baseline will contribute to the derivation of the LOCF endpoint value, markedly abnormal post-baseline value, and best/ worst case value where required

Document:

\

Author:

Version Number:

Final 1.0

Version Date:

24FEB2020

Template No: CS_TP_BS016 Revision 4
Effective Date: 01Apr2016

Reference: CS_WI_BS005

(e.g. shift tables).

In the case of a retest (same visit number assigned), the latest available measurement for that visit will be used for by-visit summaries.

Early termination data collected post baseline will be assigned to the next planned visit for that assessment. This mapping will be done for all data points used in the efficacy and safety analyses, except for the complete case analysis of the SAPS-PD total score and CGI-S score (see Section 15.1.4.5).

Listings will include scheduled, unscheduled, retest and early termination data.

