If subject appears to be symptomatic as assessed by the site during a telephone contact, an unscheduled visit will be made as early as possible (see Section 11.9.12).

11.9.4. Visit 7 (Study Day 43 [± 2 days], Open-label Baseline, OL Day 1)

The following procedures will be conducted during this visit:

- Prior/concomitant medications
- Study drug accountability
- Dispense Study Drug
- Physical and neurological examination
- Weight
- Vital sign measurements (prior to ECG)
- Perform standard 12-lead ECG
- Blood samples for clinical laboratory evaluation (hematology, serum chemistry, serum prolactin, HbA_{1c}, glucose panel, and lipid panel)
- Urine sample for urinalysis and urine drug screen
- Blood sample for determination of plasma SEP-363856 and SEP-363854, 12 ± 4 hours after the Day 42 dose
- Perform breath alcohol test
- SAPS-PD
- NPI
- CGI-S
- MMSE
- UPDRS II and UPDRS III
- SCOPA-DS
- SCOPA-NS
- RBDQ

- C-SSRS
- Adverse events
- Review Continuation Criteria for Open-label extension
- Administer first open-label study drug dose

After receiving the initial dose of OL study drug, subjects will remain in the clinic for at least 2 hours of clinical observation, which will include periodic assessments of orthostatic vital signs (1 hour [\pm 15 min] and 2 hours [\pm 15 min] post dose); additional medical assessments can be performed as needed per investigator discretion. Findings will be collected on appropriate case report forms (CRFs). Subjects will be discharged home if medically stable. Telephone calls to the subjects will be made on the first 2 days following the visit (see Section 11.9.11).

11.9.5. Visit 8 (Day 50 ± 2 days; OL Day 8),

The following procedures will be conducted during this visit:

- Concomitant medications
- Study drug accountability
- Dispense Study drug
- Vital sign measurements (prior to ECG)
- NPI
- CGI-S
- MMSE
- UPDRS II and UPDRS III
- C-SSRS
- Adverse events

If the subject titrates up, the subject will remain in the clinic for at least 2 hours of clinical observation, which will include periodic assessments of orthostatic vital signs (1 hour [\pm 15 min] and 2 hours [\pm 15 min] post dose); additional medical assessments can be performed as needed per investigator discretion.

A telephone calls to the subjects will be made on the first 2 days after a dose adjustment (increase or decrease) (see Section 11.9.11).

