12.2. Objective Findings

Clinically significant abnormal objective findings (eg, clinical laboratory value, ECG value, and physical examination observation) will also be recorded as AEs.

When a clear diagnosis is available that explains the objective findings, this diagnosis will be recorded as the AE, and not the abnormal objective finding (eg, viral hepatitis will be recorded as the AE, not transaminase elevation). If a definite diagnosis is not available, then record the sign (eg, clinically significant elevation of transaminase levels) or symptom (eg, abdominal pain) as the AE.

Clinical laboratory test results will be reviewed by the Investigator. The Investigator must determine the clinical significance of all out of range values. Clinical laboratory test with possibly drug-related or clinically relevant abnormal values of uncertain causality may be repeated. Any abnormal values that persist should be followed at the discretion of the Investigator. Laboratory reports will be initialed and dated on all pages by the Investigator.

Clinical Laboratory Tests Outside the Normal Range: Any value outside the normal range will be flagged for the attention of the Investigator or appropriate designee at the study center. The Investigator or appropriate designee will indicate whether or not the value is of clinical significance. Additional testing during the study may be done if medically indicated. If a clinically significant abnormality is found in the samples taken after dosing, during the study, and/or at the Follow-Up Visit, this should be recorded as an AE and the subject will be followed until the test(s) has (have) normalised or stabilised.

All on-site ECG tracings and ECG over-read reports will be reviewed by the Investigator. The Investigator must determine the clinical significance of all abnormal ECGs. ECG with possibly drug-related or clinically relevant abnormal findings of uncertain causality may be repeated. Any abnormal ECGs that persist should be followed at the discretion of the Investigator. ECG tracings will be initialed and dated on all pages by the Investigator.

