21. APPENDIX II. CLINICAL LABORATORY TESTS

Detailed instructions will be provided in a study center manual. The following clinical laboratory tests are to be performed:

Clinical Safety Panel

HEMATOLOGY: (Differential reported as % and absolute value)

Hemoglobin, Hematocrit, Platelet Count, Red Blood Cell (RBC) Count, white blood cell (WBC) - Total Count, WBC Differential, (Basophils, Eosinophils, Lymphocytes, Monocytes, Neutrophils), RBC morphology

BLOOD CHEMISTRIES: Alanine aminotransferase (ALT), Alkaline Phosphatase (ALP), Aspartate aminotransferase (AST), Bicarbonate (CO₂), Bilirubin (Total, Direct, Indirect), Blood Urea Nitrogen (BUN), Calcium (Ca), Chloride (Cl), Creatinine, Glucose, Creatine phosphokinase (CPK), Magnesium (Mg), Phosphorus (P), Potassium (K), Protein (Total), Sodium (Na), Uric Acid, Albumin

URINALYSIS: Blood, Glucose, Ketones, Leukocyte esterase, Microscopic examination, Nitrites, pH, Protein

COAGULATION PANEL: International Normalized Ratio (INR), Partial Thromboplastin Time (PTT), Activated Partial Thromboplastin Time (aPTT)

LIPID PANEL: LDL-Cholesterol, HDL-Cholesterol, Triglycerides

THYROID PANEL: Thyroid stimulating hormone (TSH)

URINE DRUG SCREENING: Amphetamines, Barbiturates, Benzodiazepines, Cannabinoids, Cocaine, Methamphetamines, Methadone, Methylenedioxymethamphetamine (MDMA), Phencyclidine (PCP), Opiates, Oxycodone

OTHER TESTS: Serum Pregnancy (β-hCG) (in female subjects only) Glycosylated hemoglobin (HbA_{1c}), serum follicle stimulating hormone (FSH), prolactin, breath alcohol test

Laboratory reports will be initialed and dated on all pages by the Investigator listed on the Form FDA 1572 (MD or DO). Laboratory test results will be reviewed by the Investigator as they become available. The Investigator must determine the clinical significance of all out-of-range lab values (except drug screens). Possibly drug-related or clinically relevant abnormal values of uncertain causality must be repeated. Any abnormal values that persist should be followed at the discretion of the Investigator.

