16.2. LABORATORY EVALUATIONS

Laboratory data to be reported for this study include hematology, serum chemistry (including lipid panel and thyroid panel), urinalysis, coagulation, urine drug screening, Glycosylated haemoglobin (HbA1c), serum follicle stimulating hormone (FSH), prolactin, breath alcohol test and serum pregnancy test (only listed). A list of laboratory assessments to be included in the outputs is included in Section 21/ Appendix II of the CSP.

Presentations will use international system of units (SI).

Quantitative laboratory measurements reported as “ $< X$ ”, i.e. below the lower limit of quantification (BLQ), or “ $> X$ ”, i.e. above the upper limit of quantification (ULQ), will be converted to X for the purpose of quantitative summaries, but will be presented as recorded, i.e. as “ $< X$ ” or “ $> X$ ” in listings.

The following summaries will be provided for laboratory data for DB and OL period:

- By visit summary of observed values and changes from baseline for continuous data in hematology, chemistry, and urinalysis. Prolactin results will be summarized separately by gender. Glucose and lipid panel results will be summarized separately by fasting status.

Document:

\

Author:

Version Number:

Final 1.0

Version Date:

24FEB2020

Template No: CS_TP_BS016 Revision 4
Effective Date: 01Apr2016

Reference: CS_WI_BS005

- By visit summary of the number and percentage of subjects in each outcome category for categorical data in urinalysis and urine drug screening (if applicable). For urine drug screening, the results will be reported as "Positive"/ "Negative".
- Shift in lab results (chemistry, hematology, urinalysis) from baseline to Week 6 in DB period, and from baseline to post-OL baseline visits in OL period according to the reference range criteria provided by the central laboratory.

For the OL extension period, both the DB baseline and the OL baseline will be used in the calculation of change from baseline values, and for shift from baseline.

All laboratory data will be provided in data listings for DB period and OL period, with the values outside the reference ranges and that meet potentially clinically significant (PCS) criteria shown in Appendix 4 flagged.

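### SAP 6.4 lets an abnormality-prompted repeat labelled Visit 7, possibly taken after open-label dosing, replace the double-blind Week 6 laboratory or ECG value

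*SAP*

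**What the plan says.** SAP 6.4 treats three kinds of value differently.

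- **Retests under the same visit number:** "In the case of a retest (same visit number assigned), the latest available measurement for that visit will be used for by-visit summaries". Nothing is said about whether the first value was valid, or about timing relative to dosing.
- **Unscheduled values:** "Unscheduled measurements will not be included in by-visit summaries". However, "Unscheduled measurements collected post baseline will contribute to the derivation of the LOCF endpoint value, markedly abnormal post-baseline value, and best/ worst case value", and shift tables are given as the example of that use. Retests are not named there.
- **Listings:** "Listings will include scheduled, unscheduled, retest and early termination data".

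SAP 6.5 analyses data by the visit recorded on the CRF and, apart from early-termination mapping, applies no windows. SAP 6.2 takes the Visit 7 measurement as open-label baseline and asks for time information to be used in deriving baselines where it exists. Only for weight, BMI, SAPS-PD and CGI-S does SAP section 10 say that the open-label baseline must precede the first open-label dose.

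SAP 16.2 plans by-visit summaries and a "Shift in lab results (chemistry, hematology, urinalysis) from baseline to Week 6 in DB period". Laboratory PCS criteria only flag listings. SAP 16.3 plans by-visit ECG summaries and a shift in overall assessment to Week 6. Its QTc outlier counts use any post-baseline value.

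On repeats, Protocol Appendix II says "Possibly drug-related or clinically relevant abnormal values of uncertain causality must be repeated". Protocol 12.2 makes the laboratory repeat optional and says "ECG with possibly drug-related or clinically relevant abnormal findings of uncertain causality may be repeated". Table 2 schedules double-blind laboratory panels and ECGs at Visits 1, 3 and 7. The Visit 7 procedures (Protocol 11.9.4) end with "Administer first open-label study drug dose".

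**The concern.** A rule that keeps the latest value is harmless if repeats happen at random. Here they are prompted by abnormality, so the substitution runs one way: an abnormal value can be replaced by its repeat, which tends back towards normal, while normal values stay as they are.

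In the double-blind period there is one scheduled post-baseline point, so no other visit dilutes the substitution. Both arms also start open-label SEP-363856 at that visit. A later repeat filed as Visit 7 would be an on-drug value shown as double-blind Week 6, including for subjects randomized to placebo. The Week 6 laboratory displays are the main tabulated comparison of laboratory values between the arms, with about 24 and 12 subjects, so one or two substitutions would be visible.

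**Working it through.** The plan gives no figure for this point, so the check is a trace of the rule followed by an illustration.

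**1. Trigger.** Both protocol passages tie repeats to abnormal findings that may be drug-related or clinically relevant. Normal values have no trigger. The two passages disagree on whether the laboratory repeat is required or optional.

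**2. Timing.** Laboratory samples go to a central laboratory (Protocol 11.4.2), and turnaround is not stated. A repeat prompted by a central Visit 7 result probably follows the open-label dose, but that is an inference. ECGs are reviewed by the investigator after collection (Protocol 11.4.4), so a repeat before dosing is possible.

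**3. Label.** The documents do not say whether a repeat of a Visit 7 test carries the Visit 7 number or is recorded as unscheduled. If it is unscheduled, the first value stays in the by-visit summary. If it is Visit 7, it replaces the first value.

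**4. Reach, when the repeat is labelled Visit 7.**

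| Output | Is the first value kept? |
|---|---|
| Laboratory and ECG by-visit means (16.2, 16.3) | No |
| By-visit categories: urinalysis, ECG overall assessment | No |
| Baseline-to-Week 6 shift tables | Unclear: tied to a visit, and 6.4 names worst-case use only for unscheduled values |
| QTc outlier counts (16.3) | Yes |
| Flagged listings (6.4, 16.2) | Yes |
| AE tables | Yes, if judged clinically significant (Protocol 12.2) |

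The AE route has a gap. SAP 16.1 confines double-blind AEs to those before the first open-label dose, so a Day 43 finding without a clock time may be counted as open-label.

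**5. Illustration for abnormal rates.** Assumptions, none from the documents:
- First value X and repeat Y are bivariate normal with SD 1 and correlation r.
- The upper limit is 1.96; the mean is 0 on placebo and 1 on active.
- Every out-of-range value is repeated under the Visit 7 number.
- The open-label dose has no effect.
- SAP 6.4 governs the shift table.

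Rate on the first value = 1 − Φ(1.96 − mean): placebo 0.025, active 1 − Φ(0.96) = 0.169. Difference 0.169 − 0.025 = 0.144.

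Rate on the latest value = P(X and Y both above the limit). Share returning to normal = 1 − (latest rate / first rate).

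| r | Returning, placebo | Returning, active | Latest rate, active | Latest rate, placebo | Difference |
|---|---|---|---|---|---|
| 0.9 | 41% | 27% | 0.124 | 0.015 | 0.109 |
| 0.8 | 56% | 38% | 0.105 | 0.011 | 0.094 |
| 0.7 | 67% | 46% | 0.091 | 0.008 | 0.082 |

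If only a fraction f of out-of-range values is repeated under the Visit 7 number, independently of the value, the reported difference is (1 − f) × 14.4 + f × the fully repeated figure. At f = 20% (assumed):
- r = 0.9: 11.52 + 0.2 × 10.9 = 13.7 points
- r = 0.8: 11.52 + 0.2 × 9.4 = 13.4 points
- r = 0.7: 11.52 + 0.2 × 8.2 = 13.2 points

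**6. Illustration for counts and means.** A second simulation assumes true out-of-range rates of 15% on active and 5% on placebo, again with every such value repeated. The first values give 24 × 0.15 = 3.6 active and 12 × 0.05 = 0.6 placebo subjects.

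| r | Active, of 24 | Placebo, of 12 | Fall in active mean (SD) | Fall in placebo mean (SD) |
|---|---|---|---|---|
| 0.9 | 2.6 | 0.38 | 0.609 − 0.586 = 0.02 | 0.001 + 0.010 = 0.01 |
| 0.7 | 1.9 | 0.24 | 0.607 − 0.538 = 0.07 | 0.000 + 0.031 = 0.03 |
| 0.5 | 1.4 | 0.15 | 0.609 − 0.493 = 0.12 | 0.002 + 0.050 = 0.05 |

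The difference in means therefore shrinks by only about 0.01 to 0.06 SD. Abnormal rates are affected far more than means. Neither illustration estimates the effect of on-drug values appearing under placebo; the documents give nothing to base one on.

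**The case against.** The strongest reply is that the chain has several links the documents do not state. A repeat prompted by a later central report needs a return to clinic. The protocol's unscheduled visit (11.9.12) includes an ECG and, as needed, laboratory samples, so such a repeat would naturally be recorded as unscheduled and would leave the Week 6 value alone. The retest rule names by-visit summaries, not shift tables, and 6.4 mentions shift tables as a worst-case use. Not every out-of-range value qualifies for a repeat. SAP 6.2 says times are used for baselines. Safety data are descriptive in an exploratory trial of 36 subjects.

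Much of this stands, and it limits the point. It does not remove it. SAP 6.4 itself provides for retests under the same visit number, 6.5 follows the CRF visit label, and nothing requires the repeat to precede the dose. The worst-case sentence covers unscheduled values only. The statement on times in 6.2 sets no pre-dose condition for the open-label baseline, whereas section 10 does so for four other measures.

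A reader might infer that the rule hides double-blind safety signals, or that Visit 7 repeats are necessarily on-drug. The documents support neither. QTc outlier counts, listings and AE recording keep the first value, and post-dose timing is likely only for central laboratory results. Nor do they show that the original should always be preferred to a repeat taken before the dose; that is largely a convention.

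**Conclusion.** The gap is real but conditional. For a repeat carrying the Visit 7 number, SAP 6.4 replaces the Week 6 laboratory or ECG value in by-visit summaries, and may do so in the Week 6 shift tables. Because repeats follow abnormal results, the effect is to understate double-blind abnormalities. Because open-label drug starts at that visit, on-drug values can be shown under placebo. The exposure is mainly laboratory abnormalities not judged clinically significant, which have no summary table elsewhere.

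The size cannot be determined from the documents. The fall from 14.4 to 10.9, 9.4 or 8.2 points is an upper bound with respect to repeat frequency at the assumed correlations. It requires universal repetition under the Visit 7 number and 6.4 applying to shift tables. At a 20% repeat rate the loss is about 1 point. The change is worth making because it is specific and cheap, and it extends a pre-dose condition the SAP already uses.

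**What to change.** - **SAP 6.4 and 6.2:** restrict Week 6/Visit 7 double-blind summaries, and the laboratory and ECG open-label baseline, to values taken before the first open-label dose, as section 10 already does for weight, BMI, SAPS-PD and CGI-S. Assign later repeats to the open-label period as unscheduled.
- **SAP 16.2 and 16.3:** base the double-blind shift on the worst post-baseline value before the first open-label dose, including originals, retests and unscheduled values.
- **Dose time:** use the recorded date and time of the first open-label dose. The note under Protocol Figure 1 places that dose in the evening, while 11.9.4 has it given at the visit; these passages must be reconciled.
- **Repeat trigger:** Protocol 12.2 and Appendix II must also be reconciled on whether a laboratory repeat is required or optional.

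The cost is SAP wording and one derivation flag. The safety tables may look slightly less favourable.

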6.5. WINDOWING CONVENTIONS

All data will be analyzed according to the schedule outlined in the CSP and according to the visit denoted on the case report form (CRF). Apart from early termination data (see Section 6.4), no visit windowing will be performed during the analysis for this study.

6.6. STATISTICAL TESTS

All statistical inference, unless otherwise stated, will be performed with 2-sided tests at the significance level of 0.05 and 2-sided 95% confidence intervals (CIs), unless otherwise specified in the description of the analyses.

6.7. TREATMENT GROUPS

There are several doses administrated in this flexibly-doses study but statistical analysis will describe/analyze Placebo group versus SEP-363856 all doses pooled. Apart from some exposure tables, no analysis will be performed by doses received.

6.8. STUDY MEDICATION

In this SAP, study medication refers to double-blind medication as well as open-label medication.

6.9. SUBJECTS ON-PERIOD

The SAPS-PD, CGI-S, MMSE, UPDRS II, UPDRS III, and neurological exam should be performed during the subject's on-periods (i.e., at a time when the subject shows no clinical evidence of worsening in their Parkinson's symptoms, as determined by the site investigator). Also, the NPI should be completed referencing the subject's on-period.

Regarding those scales, for statistical analysis, only the subjects on-period assessment will be taken

Document:

\

Author:

Version Number:
Version Date:

Final 1.0
24FEB2020

Template No: CS_TP_BS016 Revision 4
Effective Date: 01Apr2016

Reference: CS_WI_BS005

into account. Any assessment not done during subjects on-period will be considered as missing for statistical analysis. For data listings, all values will be listed and the variable subjects on-period will also be presented.

6.10. COMMON CALCULATIONS

For quantitative measurements, change from baseline will be calculated as:

- Value at visit X – baseline value

Percentage change from baseline will be calculated as:

- $(\text{Value at visit X} - \text{baseline value}) * 100 / (\text{baseline value})$

6.11. SOFTWARE VERSION

All analyses will be conducted using SAS version 9.4 or higher.

7. STATISTICAL CONSIDERATIONS

7.1. ADJUSTMENTS FOR COVARIATES AND FACTORS TO BE INCLUDED IN ANALYSES

The following covariates are used in the analyses. For details of their inclusion in the models, see specific analysis sections.

- Baseline value of the variable to be analyzed

